3.2. Study Outcome Measures

3.2.1. Primary

To measure **drug efficacy** as per standard parasitological endpoints including a) Cure Rate as defined by the proportion of children who have zero eggs per gram of stool as assessed by Kato-Katz four weeks following treatment and b) Egg reduction Rate as defined by the percent reduction in egg burden from baseline to four weeks post treatment as assessed by Kato-Katz.

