1. *Screening* We propose to employ a two stage screening process. The first phase is a village - based survey to identify children who are infected using rapid point of care testing (urine Circulating Cathodic Antigen (CCA)). CCA provides a highly sensitive and efficient means to screen children, with high sensitivity demonstrated in young children.^{18,19 20,21} Two stool samples (taken on consecutive days) will also be collected from every child who is CCA positive prior to the start of the study, at four weeks +/-1 week after treatment, and at 12 months post-treatment to provide a measure of infection intensity. Fecal smears will be prepared from each sample in duplicate applying the thick Kato-Katz technique for the detection of *S. mansoni*, *S. japonicum* and soil-transmitted helminths. Mean egg counts per gram of stool (epg) will subsequently be calculated and three intensity categories will be considered for *S. mansoni* and *S. japonicum* infection: light (1-99 epg), medium (100 – 399 epg) and heavy (>400 epg) as per World Health Organization Guidelines.²²

The second phase of screening will occur at the field laboratories in Palo, Leyte, The Philippines and in Lake Albert, Uganda. Prior to study enrollment, each child will undergo a physical exam and medical history to determine eligibility. Children who are not eligible based on severe malnutrition (WHZ < -3.0), severe anemia (hemoglobin < 7.0 g/dL) or chronic medical condition as defined by a disease lasting longer than three months and impacting a child's daily function or normal activities will be excluded at this stage.²³

1. *Study visit 1/Baseline.* After determination of eligibility, subjects will be enrolled following all screening assessments. Both field stations have a patient intake area with private areas for consenting and physical examinations. At this visit, a small blood drawing catheter will be placed to minimize the number of times children need to have a needle stick. Blood will be drawn for baseline morbidity studies (5 ml). In depth measures of nutritional status will be made, and children will be randomized to receive either 40 mg/kg or 80 mg/kg of Praziquantel either annually or six-monthly (4 arms).

In addition, children will be randomly split into two groups, half will have an extra 7 ml of blood drawn at the time of the morbidity studies (N=150) for immunologic studies and half will take part in pharmacokinetic studies (N=150, further details below).

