5. STUDY ENROLLMENT AND WITHDRAWAL

5.1. Subject Inclusion Criteria

- *S. mansoni* (Uganda) or *S. japonicum* (Philippines) infection of any intensity as determined by Kato-Katz
- Otherwise healthy as determined by history and physical examination conducted by the study physician at the second stage screening
- Age 12-47 months inclusive
- Parental consent to participate.

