11. STATISTICAL CONSIDERATIONS

11.1. Study Hypotheses

Primary outcome

The null hypothesis that there is no difference in cure rate assessed by microscopy at 4 weeks between children who received 40 mg/kg praziquantel and children who received 80 mg/kg praziquantel. This will be tested against the alternative hypothesis that there is a difference in cure rate at 4 weeks between children who received 40 mg/kg praziquantel and children who received 80 mg/kg praziquantel, and will be a superiority comparison.

Secondary outcomes

All secondary outcomes will be superiority comparisons, with alternative hypothesis of a difference in the outcome between the two sets of participants being compared.

For outcomes 1 to 5 below, the null hypothesis is that there is no difference in the outcome between children in the 40 mg/kg praziquantel group and children in the 80 mg/kg praziquantel group.

1. Mean egg reduction rate at 4 weeks
2. Schistosomal antigenic clearance assessed by CCA at 4 weeks
3. Schistosomal antigenic clearance assessed by CAA at 4 weeks
4. Prevalence of any adverse event within 3 hours of dosing

Adverse events will be classified by type. Adverse event types that occur with overall prevalence >5% or at prevalence >5% in either setting will also be tested for differences between trial arms.

5. (a) Prevalence of adverse event type 1 within 3 hours of dosing
(b) Prevalence of adverse event type 2 within 3 hours of dosing
(c) Prevalence of adverse event type 3 within 3 hours of dosing
continued for all adverse event types occurring with prevalence >5%

For secondary outcomes 6 to 13 below, two null hypotheses will be tested. The first null hypothesis is that there is no difference in the morbidity outcomes between children who received six-monthly praziquantel (either 40 mg/kg or 80 mg/kg) and children who received 12-monthly praziquantel (either 40 mg/kg or 80 mg/kg). The second null hypothesis is that there is no difference in the morbidity outcomes between children who received 40 mg/kg praziquantel (regardless of dosing schedule) and children who received 80 mg/kg praziquantel (regardless of dosing schedule).

6. Mean weight-for-height z-score at 12 months
7. Proportion with weight-for-height z-score at 12 months < -2
8. Mean MUAC-for-age z-score at 12 months
9. Proportion with MUAC-for-age z-score at 12 months < -2
10. Mean height-for-age z-score at 12 months
11. Proportion with height-for-age z-score at 12 months < -2

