11.4. Analysis Plan

A trial flow chart will be constructed, showing the number of children screened, enrolled and randomised, together with reasons for exclusion at each stage. Baseline characteristics of trial participants will be summarised by trial arm. Numbers and proportions will be reported for categorical characteristics. Means, standard deviations, medians and ranges will be used for continuous characteristics.

All trial analyses will be done using the intention-to-treat population, i.e. all children will be included as randomised, regardless of whether or not they received the allocated treatment. Children will contribute to 4 week outcomes if they are assessed within 1 week of the 4 week time point. Children will contribute to 6 and 12 month outcomes if they are assessed within 2 weeks of these time points. Since loss to follow-up is expected to be low at 4 weeks, only children for whom outcome data are available will be included in analyses (complete case analysis), with no imputation of missing outcome data planned.

The primary outcome of cure rate will be compared between trial arms using a chi-squared test statistic. The difference in proportions cured and a corresponding 95% confidence interval will be calculated. The related primary outcome, egg reduction rate, is defined as the percentage decrease in egg count between baseline and follow-up. The mean egg reduction rate will be compared between trial arms using a t-test, with the difference in mean egg reduction rate and its 95% confidence interval calculated. Schistosomal (CCA and CAA) antigenic egg clearance outcomes will be analyzed using the same approach as for cure rate (based on microscopy).

Prevalence of adverse events (both any and separately for types of event that occur with overall prevalence >5%) will be compared between trial arms using chi-squared tests. Rare adverse events will be tabulated by trial arm but no formal statistical comparisons done. Severity of adverse events will also be tabulated, by trial arm.

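### The t-test on mean egg reduction rate works on each child's percent change, which has no lower limit, so a few mostly lightly infected children can dominate the estimate and much of the power can be lost

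*Combined protocol and SAP*

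**What the plan says.** Section 3.2.1 lists two primary measures, cure rate and "Egg reduction Rate as defined by the percent reduction in egg burden from baseline to four weeks post treatment". It does not say whether the percentage is taken per child or per group.

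Section 11.4 calls it a related primary outcome: "egg reduction rate, is defined as the percentage decrease in egg count between baseline and follow-up". It then states "The mean egg reduction rate will be compared between trial arms using a t-test", with a 95% confidence interval for the difference in means. No floor, transformation, count model or rule for a child whose count rises is given.

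Section 11.1 lists "Mean egg reduction rate at 4 weeks" as the first secondary outcome, so the documents disagree on its rank.

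Section 5.1 admits "infection of any intensity as determined by Kato-Katz". The screening text in section 4 sets the intensity bands at "light (1-99 epg), medium (100 – 399 epg) and heavy (>400 epg", so very small baseline counts are eligible.

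On measurement, section 4 says "Two stool samples (taken on consecutive days) will also be collected from every child who is CCA positive" and "Fecal smears will be prepared from each sample in duplicate applying the thick Kato-Katz technique". That is four smears at baseline.

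**The concern.** An egg reduction rate computed for a whole group gives one number per arm, and a t-test cannot be run on that. The only workable reading of section 11.4 is one percentage per child, averaged. That percentage has the child's own baseline count as its denominator. Cured children all score exactly 100%. An uncured child with a small baseline count can score minus several hundred or several thousand percent, because egg counts vary from day to day.

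Two things are at stake. The first is meaning: a reader will take the result as the fall in egg burden, and an average of individual ratios need not be close to that. The second is precision: a few extreme values can inflate the standard deviation and hide a real dose effect on an outcome that three sections (3.1.1, 3.2.1 and 11.4) treat as primary. Section 11.4 also plans to examine egg reduction rate by baseline intensity, and the low-intensity stratum is where the ratio is least stable.

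**Working it through.** **Plan's own figures.** The documents give no standard deviation, effect size or power for egg reduction rate. Section 11.2 rests on cure alone: 70% v 82%, two-sided 5%, 7% loss, N=600. That is 300 per dose group, and 300 × 0.93 = 279 evaluable. With 279 per group the chi-squared test of 70% v 82% has 91.5% power. (The stated 173 and 232 per arm are below the 198 and 265 that the usual formula gives, but 279 exceeds both. That is a separate matter.)

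**Bounds.** Individual rate = 100 × (1 - follow-up/baseline).
- Follow-up 0: 100 × (1 - 0) = +100%, the maximum.
- Follow-up above baseline: negative, with no limit.

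**Leverage of one child.** Assume 24 epg per egg on one smear. One egg over four smears is then 24/4 = 6 epg.
- 6 to 300 epg: 100 × (1 - 300/6) = -4900%. In place of a typical child at about 90%, the group mean moves by (-4900 - 90)/279 = -17.9 points.
- 10 to 200 epg: 100 × (1 - 200/10) = -1900%. The mean moves by (-1900 - 90)/279 = -7.1 points.

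**Simulation.** All distributional inputs are assumptions: lognormal baseline with at least one egg seen, two stools × two smears at each time, gamma day-to-day variation, and *measured* cure set to 70% v 82%. (Sections 7.2 and 7.4 give three stools in some cases, so the smear count is itself an assumption.) There were 279 children per dose group and 600 trials per scenario, so simulation error is about 2 points. Four of the seven scenarios:

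| Baseline geometric mean (epg); log-SD; gamma shape; residual egg fraction if uncured | Mean of children's rates v group rate, at 70% cure | t-test power, 80 mg/kg changes cure only | t-test power, residual eggs also halved |
|---|---|---|---|
| 50; 1.2; 1; 0.3 | 64% v 80% | 28% | 73% |
| 100; 1.5; 0.5; 0.3 | 42% v 81% | 18% | 50% |
| 200; 1.5; 1; 0.1 | 90% v 95% | 28% | 76% |
| 300; 1.0; 3; 0.1 | 95% v 96% | 63% | 99% |

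Across all seven cure-only scenarios, power was 18-31% in six. In the seventh (heavier, steadier counts) it was 58% and 63% on two runs.

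Other results:
- In the noisier cure-only scenarios, 1-9% of children had a negative rate. The five most extreme of 2 × 279 = 558 children carried 72-86% of the within-arm variance (46% in the low-noise scenario).
- Of children below -100%, 77-90% had a light baseline (<100 epg).
- Removing the five most negative children changed the test's verdict in 25-37% of cure-only trials, and in 1-40% when residual eggs were also halved.
- The difference in means pointed the wrong way in 8-16% of cure-only trials (3% with low noise).
- With no dose effect, in the one scenario run, the t-test rejected 3.2% of the time.

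**Alternatives on the same cure-only data.** The t-test with rates floored at 0 had 50-82% power. A linear model of log(epg+1) adjusted for baseline had about 90%. Chi-squared on cure had 91-94%.

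**The case against.** The documents contain no egg-count distribution, so nobody can say from them how many children will have tiny baseline counts. Section 5.1 permits any intensity but gives no frequencies. A reader might infer that a handful of children will decide the result, or that power is mostly gone. The documents do not support either as fact: with heavier, steadier counts the cure-only power is 58-63%, and if 80 mg/kg also lowers residual eggs it is 50-99%. Section 11.2 itself expects 80 mg/kg to do better than the contrast used for sizing. This objection stands, and it is why a range is given.

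A reader might also infer that children with zero baseline eggs will be enrolled. Sections 5.1 and 14.3 require infection confirmed in stool. Only section 7.2, which treats an antigen-positive child as positive and potentially eligible, leaves room for such a child. That is a contradiction to reconcile, not an established case.

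The alternatives are not free gains. Group-level egg reduction rate restores meaning but little power: in simulations that applied 70% v 82% as true rather than measured cure, a permutation test of it had 18-21% power against 15-18% for the t-test. Those levels understate power, so only the comparison between them is useful. The log model's power is close to that of the cure test because, with 70-82% zeros, it largely contrasts zero with non-zero. It targets a different quantity.

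Finally, section 11.4 defers full details to a formal SAP before database lock. That gives an opportunity to correct the analysis, but the test and the quantity compared are already stated.

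**Conclusion.** The concern holds in a limited form. As written, the analysis *can* be dominated by a few, mostly lightly infected children, *can* differ widely from the fall in egg burden that it is meant to measure (42% v 81% in the worst scenario shown, 95% v 96% in the best), and *can* lose much of its power. The bounds and the size of a single child's effect are arithmetic. The power ranges (roughly 18-63% if only cure changes, 50-99% if residual eggs also fall) rest on assumed baseline intensity, day-to-day variation and residual egg output, with measured cure of 70% v 82% and 279 children per dose group.

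A reader might suspect a raised false-positive rate. The one null scenario run gave 3.2%, so the harm found is an unstable estimate and lost power. The cure comparison, which alone sizes the trial, is untouched.

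**What to change.** Before unblinding, replace the t-test on individual percentages. Section 11.3.1 unblinds the trial statistician for a look at the primary outcome at about 20% randomised, so the change should precede that look if it has not yet taken place.

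1. **Estimate.** Define egg reduction rate per dose group as 1 - mean(follow-up epg)/mean(baseline epg), with a bootstrap 95% confidence interval for each dose and for the difference. This matches section 3.2.1.
2. **Test.** Use a baseline-adjusted model of 4-week counts, such as a linear model of log(epg+1) on dose, log baseline epg and site, reported as a geometric-mean egg reduction rate. Add one sensitivity run with a different offset.
3. **State the limits.** The geometric-mean form is a different estimand that partly repeats the cure comparison. The arithmetic form improves interpretability rather than power.
4. **Reconcile eligibility.** Sections 7.2 and 5.1 must agree. A child enrolled on antigen alone with no baseline eggs has no defined egg reduction rate, and no log baseline for the model.
5. **Reconcile rank.** Sections 3.2.1 and 11.4 call the outcome primary, and section 11.1 calls it secondary.

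The cost is SAP and protocol wording, analysis code and one extra sensitivity run. No data collection changes.

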Three events were denoted “severe” (vomiting (2) and vertigo) in the 75 mg/kg dose group which had N = 45 children; no Serious Adverse Events as defined by death, life threatening event, need for hospitalization, or persistent morbidity/incapacity, were reported in either group. The reported rates of adverse events were slightly higher in the 75 mg/kg group than the 40 mg/kg comparison group. In a separate recently published study in Cote D’Ivoire, escalating doses of praziquantel (20, 40, 60 mg/kg) were examined in a cohort of children including pre-school age children (PSAC) aged 2-6 years.¹² Among PSAC, adverse events were mild with fewer adverse events observed three hours post-treatment compared to pre-treatment. Importantly, the number of adverse events was similar among the three praziquantel treatment doses, with fewer adverse events observed in the placebo-treated groups. Only mild expected adverse events were reported with the exception of one moderate grade adverse event 3 hours after the first praziquantel dose in one PSAC (diarrhea). No serious adverse events were noted at any dose. We will minimize risk by “admitting” children for observation with active and passive assessment for adverse events for 12 hours. We will also provide children with a meal to minimize side effects. **Finally, we will administer the 80 mg/kg dose as two doses of 40 mg/kg split over three hours.**

There is also a small risk to young children from blood draw, which is due to iron deficiency anemia as a blood draw removes red blood cells and iron. This risk is minimal given the small amount (7 – 12 ml) that will be drawn at each of three time points, representing 20 – 25 ml in a year. For the immunology study subpopulation, an extra blood draw of 7ml will be made at 4-week follow up time point. Very minimal risks are associated with venipuncture itself, which will be performed by trained medical personnel.

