- Moderate (Grade 2): Events result in a low level of inconvenience or concern with therapeutic measures. Moderate events may cause some interference with functioning and daily activities.
- Severe (Grade 3): Events interrupt the subject's daily activities and may require systemic drug therapy or other treatment. Severe events are usually incapacitating.

Changes in the severity of an AE should be documented to allow an assessment of the duration of the event at each level of intensity to be performed. Adverse events characterized as intermittent require documentation of onset and duration of each episode.

Relationship to Study Products: The assessment of the relationship of an AE to the administration of study product is made only by those with the training and authority to make a diagnosis based on all available information at the time of the completion of the eCRF. Whether the AE is related or not, is not a factor in determining what is or is not reported in this trial. If there is any doubt as to whether a clinical observation is an AE, the event should be reported.

In a clinical trial, the study product must always be suspect. To help assess, the following guidelines are used.

- **Related** – There is a reasonable possibility that the study product caused the adverse event. Reasonable possibility means that there is evidence to suggest a causal relationship between the study product and the adverse event.
- **Not Related** – There is not a reasonable possibility that the administration of the study product caused the event.

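### Adverse events are compared between doses only as present or absent; severity is tabulated, so no planned interval bounds the difference in severe events between 40 and 80 mg/kg

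*Combined protocol and SAP*

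**What the plan says.** Section 11.1 lists two kinds of adverse-event hypothesis for 40 versus 80 mg/kg. Outcome 4 is "Prevalence of any adverse event within 3 hours of dosing". Outcome 5 repeats this by event type, with a gate: "Adverse event types that occur with overall prevalence >5% or at prevalence >5% in either setting will also be tested for differences between trial arms".

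Section 11.4 gives the analysis. How often events occur is handled as follows: "both any and separately for types of event that occur with overall prevalence >5%) will be compared between trial arms using chi-squared tests". Then: "Rare adverse events will be tabulated by trial arm but no formal statistical comparisons done". And on grade: "Severity of adverse events will also be tabulated, by trial arm".

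Three further points bear on this:

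- **Grading.** Section 9.2.1 requires every event to be graded. A toxicity table in an appendix comes first, and a mild/moderate/severe scale (grades 1 to 3) serves events outside that table. On the fallback scale, "Severe events are usually incapacitating". Section 5.2 refers to laboratory abnormalities of grade 3 or higher, so the table may go above 3.
- **Objective.** Section 3.1.2 makes safety at the different dose regimens a secondary objective, and 3.1.2.4 singles out the safety of 80 mg/kg.
- **Prior evidence.** Section 2.3.1 reports three severe events (two of vomiting, one of vertigo) "in the 75 mg/kg dose group which had N = 45 children", in a study of children aged 10 to 15 years. It adds: "The reported rates of adverse events were slightly higher in the 75 mg/kg group than the 40 mg/kg comparison group".

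**The concern.** Each planned test treats a mild event and a severe one as the same outcome. If 80 mg/kg leaves the share of children with any event nearly unchanged but makes more of those events severe, the any-event test has little chance of showing it. The tests by type share this feature and do not pool severe events across types.

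The estimates are thin too. For cure rate and egg reduction rate, section 11.4 promises a difference with a 95% confidence interval. For adverse events it names only a test, and for severity only a table. It does not say whether that table counts events or children, or whether it shows four arms or two dose groups.

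At stake is what the trial can say about the higher dose in children aged 12 to 47 months. A non-significant any-event result could be read as no safety difference, with no prespecified bound on how much more often severe events might occur.

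**Working it through.** **No figure to reproduce.** The documents give no adverse-event rate, power or detectable difference for any safety comparison. The rates below are assumptions unless a source is named.

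**Inputs.**
- Group size: two arms of 150 per baseline dose (Table 1), so 150 + 150 = 300 per dose group.
- Two-sided 5%: stated in section 11.2 for the primary outcome, assumed here for safety.
- Severe rate at 80 mg/kg: 3/45 = 6.7% (section 2.3.1), assumed to carry over and assuming one event per child.
- Severe rate at 40 mg/kg: not given, so varied from 1% to 4%.

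**1. Strength of the signal.** The exact 95% CI for 3/45 is 1.4% to 18.3%. If the 40 mg/kg group had 0/45 severe events (count and size both assumed), Fisher's p = 0.24. If one child had all three events, the rate is 1/45 = 2.2%.

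**2. Planned any-event test.** Approximate power is Φ[(d − 1.96·s₀)/s₁], with d = p₂ − p₁, s₀ = √[2p̄(1−p̄)/300] and s₁ = √[(p₁(1−p₁) + p₂(1−p₂))/300].
- 50% v 55%: s₀ = 0.0408, s₁ = 0.0407, so Φ[(0.05 − 0.0799)/0.0407] = Φ(−0.73) = 23%.
- 30% v 35%: s₀ = s₁ = 0.0382, giving 26%.
- Equal prevalence: the test rejects at its 5% error rate, whatever happens to severity.

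**3. Severe yes/no comparison.** For 1% v 6.7%: s₀ = 0.0157, s₁ = 0.0155, so Φ[(0.0567 − 0.0307)/0.0155] = Φ(1.67) = 95%. The exact Fisher power is found by enumerating both binomials. The last column is the large-sample half-width 1.96·s₁, as a guide to the precision of the interval.

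| Severe at 40 mg/kg | Severe at 80 mg/kg | Power, normal approx. | Power, Fisher | Difference ± half-width (points) |
|---|---|---|---|---|
| 1% | 6.7% | 95% | 96% | 5.7 ± 3.0 |
| 2% | 6.7% | 80% | 78% | 4.7 ± 3.2 |
| 3% | 6.7% | 55% | 49% | 3.7 ± 3.4 |
| 4% | 6.7% | 31% | 25% | 2.7 ± 3.6 |

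If the 80 mg/kg rate is lower, Fisher power is about 69% for 1% v 4.4% and about 30% for 0.5% v 2.2%.

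**4. Would an ordinal test do instead?** Simulation of worst grade (none, 1, 2, 3) with 50% any-event prevalence in both groups, severe 1% v 6.7%, and grade 2 at 10% in both: a rank test has about 12% to 13% power, or about 28% if grade 2 also rises 5 points at 80 mg/kg. The severe-event comparison has 96%. The rank test is dominated by the many children with no event or a mild one.

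**5. Time window.** Outcome 4 runs for 3 hours from dosing. Section 4.2 gives the second administration (active at 80 mg/kg, placebo at 40 mg/kg) 3 hours after the first. If the clock starts at the first dose, both groups have had 40 mg/kg throughout the window, and no analysis within it can show a dose effect. Section 9.1 describes monitoring for 12 hours; section 4.2, under study visit 1, describes a stay of 3 to 6 hours.

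**The case against.** The strongest defence is that severity is not ignored. It is tabulated by arm, so a marked rise would be visible beside any null test. Common event types are tested and may include vomiting, which made up two of the three cited severe events. The DSMB may see data by arm (section 9.6.2), and section 11.4 defers full detail to a later SAP that is not among the documents. Objective 3.1.2.4 also names bone marrow, renal and liver toxicity, not clinical severity as such.

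Much of this is fair, and it keeps the point moderate. It does not close the gap. The tests by type are still any grade versus none. The halting rules in section 9.5 count product-related serious events and unexpected clinical events, and do not compare doses; a non-serious, expected grade 3 event triggers neither. The parent objective in 3.1.2 covers safety at both regimens. A later SAP could add the comparison, but nothing commits it to do so.

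Two stronger readings are tempting and should be resisted:
- **That the protocol's own data show severe events rising with dose.** Section 2.3.1 gives no severe count at 40 mg/kg, the children were aged 10 to 15, and three events are few. The cited study nearest in age (2 to 6 years, doses up to 60 mg/kg) found similar numbers of events across doses, all mild in preschool children apart from one moderate event.
- **That safety is tested only as any event versus none.** The tests by event type are also planned.

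**Conclusion.** The point holds as a gap in estimation. Every planned adverse-event comparison between doses is presence or absence at any grade, and severity has no planned test, estimate or interval, although the grades will be collected and the safety of 80 mg/kg is an objective.

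The size depends on rates that the documents do not give. A severe-event comparison would be informative at 300 per group if the 40 mg/kg rate is about 2% or less and the 80 mg/kg rate is near 6.7% (Fisher power 78% or more). It would be weak at 3% to 4% (49% to 25%), or if severe events are rare in both groups. Even then an interval bounds the difference to within roughly 3 to 4 points in the tabled scenarios, which the any-event test cannot do.

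A reader might also infer that an ordinal test on worst grade would be the natural repair. The simulation does not support that in the case that matters most, where overall prevalence is unchanged. Nor can one take a 0 to 3 scale for granted, since grades 1 to 3 are only the fallback for events outside the toxicity table.

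**What to change.** In sections 11.1 and 11.4, and in the SAP before unblinding:

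- Add a secondary safety outcome: the proportion of children with at least one adverse event of grade 3 or higher after baseline dosing (worst grade per child, pooled over event types), for 40 versus 80 mg/kg.
- Report the risk difference with an exact 95% CI, naming the method. An exact test is optional.
- Keep the any-event and by-type tests. Do not make a rank or proportional-odds test the main severity analysis.
- State that the severity table counts children by worst grade and shows the two baseline dose groups.
- Reconcile the 3-hour window in 11.1 with the 12-hour monitoring in 9.1, the 3 to 6 hour stay in 4.2 and the second administration at 3 hours. Say which dose starts the clock, so that the comparison covers time after the doses diverge.
- Align the 5% gate for event types: 11.1 also admits a type above 5% in either setting, while 11.4 uses overall prevalence only.

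The cost is wording in the protocol and SAP, and one further secondary safety comparison. The severity grades are already to be recorded. No added sample size is needed.
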